7.2 Procedures

All study-required procedures should occur as outlined in [Table 5](#). Excursions from the timing of assessments will be considered protocol deviations and should be recorded in the source documents along with the reason for the excursion.

For **patients receiving antibody treatment despite disease progression / relapse**, an Unscheduled Visit covering all assessments described under EOT visit should be completed **before the continuation of antibody therapy**. Blood parameters (haematology, serum chemistry) should be evaluated in the **local lab** according to local guidelines/standards of local medical practice for the administration of monoclonal antibodies. A urine pregnancy test should be performed for women of childbearing potential, prior to each infusion. Vital signs should be measured according to local practice for the administration of monoclonal antibodies. For this patient population only the **antineoplastic therapy and AEs** need to be captured in eCRF. Other procedures described in the column MOR00208 Additional Treatment will not apply for this patient population.

7.2.1 Screening followed by Enrolment (Start of IMP)

The Screening Period begins on the date the Informed Consent Form (ICF) is signed and will last for up to 28 days. The ICF must be signed prior to beginning any assessments solely for the purpose of this study. Standard of care assessments done on the day of consent (but prior to signing the ICF) do not need to be repeated solely for the purpose of screening and may be used as study data, if they meet the protocol requirements.

During screening, it is permitted to repeat on a **single occasion** the **central laboratory assessment** of serum chemistry and haematology parameters due to the variability of the parameters and their dependence on multitude of factors (e.g., hydration, muscle mass). This is, provided no safety concerns arise and that such laboratory results might have been caused by a transient, medically plausible event, which resolved spontaneously or as result of a medical intervention in the meantime (e.g., dehydration, vomiting, imaging procedure with a contrast). This procedure and the rationale behind it must be explicitly documented in source data. Such repeated assessment (once only) of the concerned parameters will not be counted as “re-screening” for that patient.

On Cycle 1 Day 1, patient eligibility must be confirmed before drug administration. Local laboratory parameters should be used for this purpose, as specified in [Section 7.2.13](#) Laboratory Assessments.

7.2.2 End of Treatment (EOT) Visit

An end of treatment visit will have to be completed for all patients, including, but not limited to the following circumstances:

- a. After disease progression / relapse, any time after start of the study treatment, provided MOR00208 will not be administered despite progression
- b. After last administration of study drugs.
- c. Withdrawal from study treatment as specified in [Section 6.9](#).

If the EOT visit is after 24 cycles (i.e., Cycle 25 onwards), only the applicable laboratory tests in the local laboratory will need to be performed.

7.2.3 MOR00208 Administration Despite Disease Progression

It is up to the investigator to decide according to the individual risk/benefit ratio if the patient should continue on MOR00208 in case of disease progression, after discussion with the Sponsor's Medical Monitor. For patients who will be administered MOR00208 despite progression of disease / relapse, an **Unscheduled Visit** including all protocol prescribed procedures for the **EOT Visit** need to be performed in order to capture the event (i.e. disease progression/relapse) for the antibody treatment to continue further. These procedures, if performed within less than two weeks preceding this visit, need not be repeated. PET/CT need not be repeated if it was performed during previous treatment cycle. Note: Central laboratory tests will need to be performed only until Cycle 24 for each patient, as applicable.

Following procedures will be performed (and documented in source) for these patients **during the period** of MOR00208 administration despite disease progression (prior to each infusion):

- a. Emergency Laboratory (Local Lab) evaluations consisting of haematology, serum chemistry according to local guidelines/standards of local medical practice for the administration of monoclonal antibodies.
- b. A urine pregnancy test for women of childbearing potential
- c. Vital signs

These patients will follow a visit schedule as mentioned under "MOR00208 Additional Treatment Phase", whereas their treatment cycle and visit numbers will be captured in a continuum with their previous applicable treatment visit, prior to disease progression. For this patient population only the antineoplastic therapy and AEs are going to be captured in eCRF. Other procedures described in the column MOR00208 Additional Treatment will not apply for this patient population.

In such cases an **EOT Visit** will take place after these patients have finally stopped receiving the antibody. At this EOT visit only anticancer therapy and AEs will be recorded. And lastly, a **Safety Follow-Up** will take place **30-Days** after last administration of MOR00208.

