6.3 Treatment with Study Drugs

Treatment consisting of **LEN** and **MOR00208** combination will be administered up to twelve 28-day cycles at specified dose levels as scheduled until disease progression, unacceptable toxicity, or discontinuation for any other reason, whichever comes first.

LEN can be given for up to 12 cycles in total. Treatment with LEN will have to be stopped after disease progression. On days when both study drugs are given together, LEN should be administered prior to MOR00208.

MOR00208 can be administered at the dose and schedule described in [Section 6.1](#) above, until disease progression, unacceptable toxicity, or discontinuation for any other reason, whichever comes first.

It is up to the investigator to decide according to the individual risk/benefit ratio if the patient should further continue on MOR00208 in case of disease progression, after discussion with the Sponsor's Medical Monitor or designee. For patients who will be administered MOR00208 despite progression of disease / relapse, an **Unscheduled Visit** including all protocol prescribed procedures for the **EOT Visit** (except the PK sample and the anti-MOR00208 antibody sample) need to be performed in order to capture the event (i.e. disease progression/relapse) for the antibody treatment to continue further ([Table 5](#)). In such cases an **EOT Visit** will take place after these patients have finally stopped receiving the antibody. And lastly, a **Safety Follow-Up** will take place **30-Days** after last administration of MOR00208.

For patients receiving antibody treatment despite disease recurrence/progression, before the administration of MOR00208, blood parameters (haematology, serum chemistry) should be evaluated in the local lab according to local guidelines/standards of local medical practice for the administration of monoclonal antibodies. A urine pregnancy test should be performed for women of childbearing potential. Vital signs should be measured according to local practice for the administration of monoclonal antibodies. For this patient population only the antineoplastic therapy after the end of study drug combination treatment and AEs need to be captured in eCRF. Other procedures described in the column "MOR00208 Additional Treatment" in [Table 5](#) will not apply for this patient population.

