6.8 Treatment Compliance

Dosing modifications due to toxicity are described in [Section 6.6.2](#).

Patients will receive MOR00208 under the direct supervision of study personnel. Each administration volume or dose will be checked and the vial/outer package code and volume or dose per administration will be recorded in each patient's eCRF as well as in the source data.

A patient will be considered compliant with the protocol if the MOR00208 dose administered is $\geq 80\%$ to $\leq 120\%$ of the assigned dosage per single infusion.

LEN is to be dispensed in 28-day cycles. Patients should return all unused or empty LEN bottles/blister packs to the site throughout the treatment period of the study, as instructed by the investigator. A patient will be considered compliant with the protocol if the LEN dose administered is $\geq 80\%$ to $\leq 120\%$ of the assigned dosage during a particular cycle.

Drug accountability will be checked by the field monitor during site visits and at the completion of the study.

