22.1.1 Treatment-emergent adverse events

An **on-treatment adverse event (or Treatment-emergent Adverse Event – TEAE)** is defined as any adverse event reported in the following time interval (including the lower and upper limits): date of first administration of any study drug; date of last administration of any study drug + 30 days.

If the last date of study drug administration is missing, on-treatment assessments/events include any assessment/event recorded in the database and which occur after the start date of study treatment. Safety summary tables including summaries of on-treatment deaths will be based only on on-treatment assessments/events.

An adverse event present prior to study drug administration but increased in severity after treatment start, will also be included as TEAE.

Events with missing onset dates will be included as TEAE if the end date is not before the start date of treatment.

Adverse events occurring or worsening later than 30 days after the date of last study drug administration or the date of completion/discontinuation of the study are defined as TEAE if these are considered to be related to the study drug.

If the start date and time of an AE are partially or completely missing, the AE will be assumed to be a TEAE if it cannot be definitely shown that the AE did not occur or worsen during the treatment-emergent period (worst case approach). Missing dates and times will not be replaced.

Thus, the following approach will be taken:

- If the start time of an AE is missing but the start date is complete, an AE will only be excluded from TEAE if start day is before day of first treatment or start day is after end day of treatment-emergent period.
- If start time and day are missing but the start month is complete, an AE will only be excluded from TEAE if start month is before month of first treatment or start month is

-
- after end month of treatment-emergent period or if stop date/time is before start of first treatment.
- If start day and months are missing but the start year is complete, an AE will only be excluded from TEAE if start year is before year of first treatment or if start year is after end year of treatment-emergent period or if stop date/time is before start of first treatment.
 - If start date is completely missing, an AE will not be excluded from TEAE unless the stop date/time is before start of first treatment.

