20.11.3 TEAEs per patient years of exposure to MOR00208

Summary across both treatment phases:

Based on the SAF, the absolute number of TEAEs (i.e., the actual number of events) by patient years of exposure will be summarized by SOC, PT and NCI-CTCAE Grade. For the summary, patient years of exposure will be defined as follows:

$[(\text{end date of the MOR00208}) - (\text{start date of MOR00208}) + 1] / 365.25$.

The TEAEs per patient years of exposure will be reported with three decimal places.

Summary by treatment phase:

Based on the SAF, the number of TEAEs (i.e., the actual number of events) by patient years of exposure to combination treatment vs. MOR00208 monotherapy treatment will be summarized by SOC, PT and NCI-CTCAE Grade. Summaries will be provided separately for the combination treatment (MOR00208 + LEN) and MOR00208 monotherapy phase.

- Exposure to the combination treatment is defined as follows:

$[(\text{Latest date when at least one of either study drug has been discontinued}) - (\text{earliest date when the patient is treated with both study drugs}) + 1] / 365.25$.

Due to the fact that patients may discontinue LEN before reaching Cycle 12 Day 21 (i.e., the time when LEN is discontinued as per protocol), combination treatment may stop before completing 12 Cycles of LEN.

- Exposure to MOR00208 monotherapy treatment is defined as follows:

$[(\text{Discontinuation date of MOR00208}) - (\text{earliest date of MOR00208 infusion after LEN has been permanently discontinued}) + 1] / 365.25$.

Due to the fact that patients may discontinue LEN before reaching Cycle 12 Day 21 (i.e., the time when LEN is discontinued as per protocol), MOR00208 monotherapy treatment may start before reaching Cycle 13 Day 1. The TEAEs per patient years of exposure will be reported with three decimal places.

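### Protocol 7.2.3 and 6.8 conflict on whether MOR00208 infusions given after progression are entered in the eCRF, which puts exposure, the TEAE window and AE rates at risk

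*Protocol*

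**What the plan says.** Protocol 7.2.3 lets the investigator, after discussion with the medical monitor, continue MOR00208 despite progression. These patients follow the visit schedule of the Additional Treatment Phase.

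Three sections then restrict what is entered for them. Section 7.2.3: "For this patient population only the antineoplastic therapy and AEs are going to be captured in eCRF". Section 6.3: "only the antineoplastic therapy after the end of study drug combination treatment and AEs need to be captured in eCRF". Section 7.2 repeats the rule. For the EOT visit held once the antibody finally stops, 7.2.3 adds: "At this EOT visit only anticancer therapy and AEs will be recorded".

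Protocol 6.8 sets a general rule with no exception for dosing after progression: "volume or dose per administration will be recorded in each patient's eCRF as well as in the source data".

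The SAP builds its safety outputs on dosing dates:

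- Section 6.3.2 defines the last administration as the last non-zero dose.
- The TEAE window (SAP 10.7.3, item 22.1.1) is "date of first administration of any study drug; date of last administration of any study drug + 30 days". A later AE counts only if it is judged related.
- Exposure to MOR00208 (8.9.2) ends a fixed interval after the last administration, and infusions are counted in the same section.
- Deaths (10.7.3.1.6) are split at 30 days after the last administration.
- In 20.11.3, "the absolute number of TEAEs (i.e., the actual number of events) by patient years of exposure will be summarized", with exposure running from the start to the end date of MOR00208. Section 23.1.1 takes its exposure from 8.9.2.

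**The concern.** A site that reads the three population-specific sections literally would enter AEs and other anticancer drugs, but no infusion date, no volume and no final stop date. The database would still hold a last MOR00208 dose, namely the one before progression, and nothing in it would show that this date is too early.

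Secondary objective 7 is the safety of the combination. AE collection continues until 30 days after the true last dose (Protocol 8.2), so the events would be in the database. What could fail is their classification against dosing, and the denominator of the exposure-adjusted rates.

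**Working it through.** The plan gives no figure to reproduce here: neither the number of patients treated after progression nor their time on drug is stated. The check is a reading of the passages, followed by an illustration.

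**1. Does other text settle the conflict?**

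| Place | What it shows | Does it settle eCRF entry of doses? |
|---|---|---|
| Protocol 6.3, 7.2, 7.2.3 | Only AEs and antineoplastic therapy are entered | Yes, read literally: no |
| Protocol 6.8 | Every administration is entered | Yes, read literally: yes |
| Table 5, footnote 17 (items waived after progression) | Not attached to the MOR00208 administration row | No. It is also absent from the vital signs, emergency laboratory and pregnancy test rows, which 7.2.3 has performed and documented in source |
| Protocol 7.2.3, continuous cycle and visit numbering | Numbers carry on after progression | No. Numbers are not dose dates or volumes |

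Table 5 shows what is done, not what is entered, so the conflict stands.

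**2. What follows in the SAP if 7.2.3 is followed?** The pre-progression dose would tend to become the last administration. Item 22.1.1 has a fallback that treats all later events as on-treatment, but only when the last-dose date is missing. It would not apply if the earlier date is taken as the last dose. No derivation in 6.3.2, 8.9.2, 22.1.1, 20.11.3 or 23.1.1 mentions dosing after progression.

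**3. One patient (all inputs are assumptions).** Recorded exposure is 10 months and unrecorded dosing lasts 6 months. The AE rate is constant at λ per month, and a share p of late AEs is judged related. The 30-day window is taken as 1 month. The 30 days after the true last dose are left out on both sides, as is the short interval that 8.9.2 adds to the last dose.

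- Exposure missed: 6/16 = 37.5%.
- TEAE window closes too early by 6 × 30.4375 = 183 days.
- AEs counted: 10λ (recorded period) + 1λ (window) + 5pλ (related only) = (11 + 5p)λ.
- Recorded rate: (11 + 5p)λ/10. True rate: 16λ/16 = λ.
- Overstatement: (11 + 5p)/10, which is 1.1 at p = 0 and 1.6 at p = 1.

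The direction depends on the constant rate. Suppose the AE rate after progression is r times the earlier rate and p = 0. The recorded rate is then (10 + r)λ/10 and the true rate (10 + 6r)λ/16. They are equal when 160 + 16r = 100 + 60r, so r = 60/44 = 1.36. Above that value the recorded rate is too low.

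**4. Whole study (all inputs are assumptions).** Let a fraction f of patients have k unrecorded months, with mean recorded exposure m. True over recorded exposure is 1 + f·k/m, and the number of patients cancels.

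| f | k (months) | m (months) | True/recorded | Exposure understated |
|---|---|---|---|---|
| 2% | 2 | 12 | 1.003 | 0.3% |
| 10% | 6 | 12 | 1.05 | 4.8% |
| 10% | 6 | 6 | 1.10 | 9.1% |
| 20% | 12 | 6 | 1.40 | 28.6% |

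Under a constant AE rate, the third numeric column is also the rate inflation if every late AE still counts as a TEAE. It is lower if some are dropped.

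**The case against.** The strongest reply is that no passage says post-progression infusions go unrecorded. Section 6.8 covers every administration, and the restriction in 7.2.3 follows a list of local laboratory tests, pregnancy tests and vital signs. It can therefore be read as limiting the entry of assessments only. The next sentence in 7.2.3 waives the other procedures in the Additional Treatment column. That column includes the dosing row, so a fully literal reading would cancel the dosing that the section exists to permit.

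The SAP also expects such data. Section 8 summarises patients treated despite progression with reasons for discontinuation, 8.9.6 lists MOR00208 dosing for the SAF, and 6.3.2 has no cut at progression. The eCRF itself, which would show whether dosing pages stay open, is not among the documents. Thinner capture after progression may also be deliberate, because other antineoplastic therapy is allowed at that stage and confounds the AEs.

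Much of this stands. A reader might infer that the exposure, TEAE and rate outputs are wrong. The documents do not support that, because the error is zero wherever 6.8 was followed. A reader might also take 1.6 as the size of the bias. It is a ceiling for one assumed patient, reached only if every late AE is judged related, whereas the planned rates count all TEAEs. Crude incidence tables divide by patients, so only the TEAE flag can change there, and total deaths are unaffected.

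What does not stand is that 6.8 resolves the matter. It is a general rule, and the three sections written for this population say that only two items are captured. Sites could reasonably follow either.

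**Conclusion.** The protocol contradicts itself on whether MOR00208 dosing after progression is entered in the eCRF, and the SAP's safety derivations need the answer. If 7.2.3 is followed:

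- exposure and infusion counts are understated;
- unrelated AEs that start more than 30 days after the last pre-progression dose are not TEAEs;
- deaths in that period are classed as post-treatment;
- rates per patient-year are distorted.

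If 6.8 is followed, nothing is wrong. The factor of 1.1 to 1.6 holds for one patient under the assumed 10 and 6 months and a constant AE rate. The study-level figures are a range over assumptions, because the documents do not say how many patients continue or for how long. The point concerns secondary objective 7 and does not touch the primary endpoint. It is worth correcting because the plan states a rule that, if obeyed, gives a wrong result, and the correction is cheap.

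**What to change.** Reconcile Protocol 6.3, 7.2 and 7.2.3 with 6.8. State that for patients continuing after progression the date and volume of each MOR00208 infusion, and the final discontinuation date and reason, are entered in the eCRF, including at the last EOT visit. For patients already treated this way, back-enter the data from source documents, where 6.8 already requires the doses, or from drug accountability records.

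In SAP 8.9.2, 22.1.1, 20.11.3 and 23.1.1, state that these infusions count toward last administration, exposure and the TEAE window. Where dates cannot be recovered, present AEs after progression separately rather than classing them by the last pre-progression dose.

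The cost is a wording change and limited data entry. There are no new procedures for patients, and no treatment rule changes.

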7.2.4 Safety Follow-up Visit

A **Safety Follow-Up** will take place **30-Days** after last administration of IMP. Following assessments will be performed and recorded in eCRF:

- a. Limited physical examination
- b. Adverse events including second primary malignancies
- c. Antineoplastic therapy

7.2.5 Survival Follow-up

After Safety Follow-up Visit, a phone call will be made to the patient (or the patient's family) every 90 days (+ 2 weeks) for to cover a duration of up to 5 years from Cycle 1 Day 1 to inquire about the patient's status, second primary malignancy (SPM) and information on any antineoplastic therapies utilised since discontinuation of study treatment. For patients who are lost to follow-up, at least three attempts of contact by the site should be made and documented in the source data.

7.2.6 Diagnostic Biopsy

Patients must be eligible and willing to undergo a biopsy of a lymph node or other pathological tissue, providing enough tumour tissue for correlative studies, as a part of participation in this study. Histological confirmation of the diagnosis of DLBCL will be performed by a central pathologist, retrospectively after enrolment. Surgically acquired tissue samples are preferred, but core biopsies are permitted. Bone marrow biopsies are not adequate for this purpose and should be performed only for disease staging.

Should it not be possible to obtain a fresh tumour tissue sample from the patient, archival paraffin embedded tumour tissue acquired \leq 3 years prior to screening for this protocol must be available for this purpose.

The local pathology report indicating DLBCL diagnosis is acceptable for determining a patient's eligibility. Central pathology review is mandatory, but retrospective in nature. Tissue samples (or archival paraffin blocks, as stated above) should be submitted within 30 days of patient enrolment in the study. Patients can be enrolled prior to submission of tissue sample(s).

In case of discrepancies between the assessments of the local and the central pathologists, the one of the central pathologist prevails. If the DLBCL diagnosis of the local pathologist cannot be confirmed by the central pathologist, and a patient's treatment has already commenced, they may remain in the study.

7.2.7 Demographic Data/Relevant Medical History and Current Medical Conditions/Baseline Stage and Prognostic Classification

Demographic variables to be recorded will include age, gender, race, body height, and body weight. Weight and height should be measured while the patient is without shoes, but dressed.

At the time of signing of the ICF, relevant medical history and current medical conditions should be recorded. The medical history of DLBCL should be documented in detail, including baseline symptoms as well as a detailed history of prior cancer therapies for DLBCL, with start and stop dates, number of therapy line(s), disease progression during or after therapy, as well as discontinuations due to intolerance or any other clinically significant illness. Any previous therapy (e.g., chemotherapy, immunotherapy, or radiation therapy) for DLBCL should be recorded in the eCRF. Also, examinations leading to the diagnosis of the latest progression of DLBCL should be documented in the patient's source documents. This may include, for example, results of laboratory examinations, imaging results, or clinical symptoms related to DLBCL. The assessment of the lymphoma should include staging. In order to reflect the patient's status at the time of enrolment, the standard staging system used for DLBCL reflecting the number of sites of involvement and their relation to the diaphragm, the existence of B-symptoms, and the presence of extranodal disease, will be documented (see [Appendix E](#) for Ann Arbor Staging).

Additionally the disease risk assessment as per IPI (see [Appendix B](#)) and patient status as per Eastern Cooperative Oncology Group (ECOG) performance status criteria (see [Appendix F](#)), will be recorded.

Examples of clinical significant systemic diseases, which may exclude patient participation include, but are not limited to:

- a) A diagnosis of a myocardial infarction within the 6 months prior to enrolment, New York Heart Association (NYHA) class II or higher congestive heart failure, uncontrolled angina pectoris, severe uncontrolled ventricular arrhythmias, clinically significant pericardial disease, or electrocardiographic evidence of acute ischaemia or significant conduction system abnormalities, in the opinion of the investigator. Patients with stable, asymptomatic atrial fibrillation are allowed in the study provided they do not meet the other cardiac exclusion criteria
- b) Systemic diseases (e.g., cardiovascular, renal, hepatic) that would in the investigator's opinion preclude participation in the study or compromise the patient's ability to give informed consent
- c) History or evidence of clinically significant peripheral nervous system, cerebrovascular, or CNS diseases, meningeal (e.g., meningeosis leukaemica), or epidural malignancy including brain metastasis or cerebrovascular event(s) with clinically significant sequelae. Screening for cerebrospinal fluid (CSF)/CNS involvement is not required but may be performed at the discretion of the investigator.

